### **8.7.2 Data collected**

See [Section 8.7.5](#).

Information specific to the sub-registry will be collected in specifically designed CRFs. Data collected by sub-registry HCPs or their designees will be submitted to the sub-registry for central processing and evaluation. A primary contact person located at the participating site should be designated as the individual responsible for completing and entering CRFs into the sub-registry database.

Selected data from the sub-registry CRFs will be monitored periodically against source documents at the treating HCP's site by a representative of Sanofi Genzyme (or its designee) to ensure data completeness and accuracy.

### **8.7.3 Site/Investigators questionnaire**

Not applicable.

Since this is a registry where data will be derived from routine clinical practice, there will be no predefined diagnostic or monitoring procedures. Interviews or questionnaires will be performed as in routine clinical practice.

### **8.7.4 Patient/Subject tracking log**

The patient/subject tracking log will be used to document the reason for non-inclusion. Data collected on this log will be fully anonymous (patient # [1, 2,...], included: Yes/No, reason for non-inclusion).

### **8.7.5 Patient data**

Note: The observational study operates under real-world clinical practice conditions. It collects only available data. There are no imposed protocol visits or procedures.

Evaluation	At enrollment	Study follow-up assessments a,c	End of study
Informed Consent Form	x		
Inclusion criteria/Exclusion criteria	x		
Demographics *	x		
CYP2D6 predicted phenotype*	x		
GD history*	x		
Clinically significant medical history with assessment of relationship to Cerdelga or Cerezyme before enrollment	x		
GD treatment history*	x		
Current GD treatment*	x b	x b	x b
All adverse events		x	x
Concomitant medications for particular cases only d	x	x	x

\* Information collected as a part of ICGG Gaucher registry assessments

- a Frequency of the follow-up visits will be as per local practice visit schedule, or following the recommended schedule of events of the ICGG Gaucher Registry. Study assessments will be performed during office visits. In exceptional cases, follow-up information (including treatment status and AEs) could be collected by phone. Adverse events should be collected from patients at least every 6 months. If the period of time between the last ELISAFE sub-registry assessment and the next planned ICGG Gaucher Registry assessment is expected to be more than 6 months, a phone call to inquire about new/ongoing AEs is recommended.
- b Any data that are already entered in the ICGG Gaucher registry will not need to be entered in the sub-registry.
- c If a patient temporarily stops (for any reason) treatment with Cerdelga or Cerezyme and the treating physician considers that the treatment can be potentially restarted, the patient can stay in the sub-registry as long as the sub-registry is open, the patient is willing to participate and is available for follow-up assessments. Collection of all AEs will be continued for the duration of 30 days after stopping Cerdelga or Cerezyme, and after that period only new SAEs will be collected and follow-up of ongoing AEs will be performed. Collection of all AEs in ELISAFE will be resumed when the patient restarts treatment with Cerdelga or Cerezyme.

- d* Any corrective treatment prescribed following the occurrence of an AE. Any concomitant medication that caused an overdose. In case of relationship of the AE/overdose/pregnancy to other concomitant medication.

Data collected in the ICGG Gaucher Registry and sub-registry to be used in this study include:

Upon enrollment into the sub-registry:

- Demographics
  - Gender and date of birth
  - CYP2D6 genotype testing result and date of blood sample collection, if available
- GD history
  - GD diagnosis confirmation
  - Date of diagnosis
  - GD type
- Primary GD treatment history:
  - Date and type of first primary GD treatment
  - Date, dose and type of all past primary GD treatments
  - Start date and dose of Cerdelga or Cerezyme treatment at sub-registry enrollment
- Date of sub-registry enrollment
- Clinically significant medical history (including AEs reported by patient and in opinion of investigator related to Cerdelga intake and Cerezyme administration which occurred prior to enrollment into the safety sub-registry).

At follow-up visits:

No experimental intervention is involved. Participating patients will undergo clinical assessments and receive treatment for GD, as determined by their treating HCPs and using the ICGG Gaucher Registry Recommended Schedule of Assessments as a guideline.

At each follow-up visit the following will be collected:

- Dosing information: including Cerdelga or Cerezyme regimen at the time of follow-up and treatment interruptions for  $\geq 1$  month or regimen changes since last visit with reasons for treatment interruptions or regimen changes.
- Adverse events: information on all AEs ongoing and occurring since the last visit, regardless of seriousness or relationship to Cerdelga or Cerezyme. Adverse events should be collected from patients at least every 6 months. If the period of time between the last ELISAFE sub-registry assessment and the next planned ICGG Gaucher Registry assessment is expected to be more than 6 months, a phone call to inquire about new/ongoing AEs is recommended.

#### **8.7.6 Procedure for withdrawal of patients from study follow-up schedule**

The participating Investigator/HCP should make every effort to re-contact the patient to determine his/her health status, including at least his/her vital status.

There is no minimum duration of participation for patients.

Any patient is free to withdraw authorization and discontinue his/her participation in the sub-registry at any time, without prejudice to further treatment. The patient's participation in the sub-registry may be discontinued at any time at the discretion of the treating HCP. The following may be justifiable (but not exhaustive) reasons for the treating HCP to remove a patient from the sub-registry:

- The patient was erroneously included in the sub-registry;
- The patient is taking an investigational product during participation in the sub-registry;
- The sub-registry is terminated by Sanofi Genzyme.

Patients who withdraw, or are withdrawn, from this safety sub-registry are still permitted to participate in the ICGG Gaucher Registry.

#### **8.7.7 Logistic aspects**

Not applicable.

## 8.8 DATA ANALYSIS

Analysis will be performed on the Safety Set, defined as all patients enrolled in the sub-registry who have received at least one dose of Cerdelga or Cerezyme following enrollment. The analysis will be performed for each treatment group and overall (where appropriate) by treatment status (if applicable).

Patient's treatment status at the time of sub-registry enrollment will be defined in three categories:

- a) Patients naive to any GD treatment (ERT or SRT). This category will include, for example, new diagnosed patients.
- b) Patients naive to the product of interest (Cerdelga in the Cerdelga group and Cerezyme in the comparator group) but experienced to any other treatment for GD (ERT or SRT). This category will include, for example, patients who will switch from any one therapy to the product of interest.
- c) Patients experienced to the treatment of interest. This category will include patients who were on treatment with the product of interest at entry into the sub-registry and then continue this therapy.

Note:

- Patients whose first GD treatment is commercial Cerdelga or Cerezyme, and who enroll in the sub-registry within 3 months of the first dose will be considered treatment naive for the purposes of analysis. Regardless of prior treatment, these patients must receive either Cerdelga or Cerezyme during their participation in the sub-registry.
- Exposure to Cerdelga in clinical studies will be considered for any patient of the sub-registry, notwithstanding the group of treatment they belong to during sub-registry participation.
- The data for enrolled patients who switch treatment from Cerdelga to Cerezyme or vice-versa during follow-up will be evaluated to and from the point of switch in the therapy.
- A subset of treatment experienced patients will be patients who will switch from any one therapy to any other therapy.
- When available, AEs reported by the patient and in the opinion of investigator related to Cerdelga intake and Cerezyme administration (prior to enrollment into the safety sub-registry) will be collected as part of the patient enrollment characteristics (medical history).

Analysis of endpoint: The main analysis of interest will be the incidence rate of any AE report for Cerdelga-treated patients during their participation in the sub-registry, considering treatment status at sub-registry enrollment (if applicable). If sufficient data within each treatment status category are collected, incidence rates within treatment status category will be estimated. Similar calculations will be performed for the Cerezyme-treated patients. Summaries will also be presented for three categories of treatment status within each of the Cerdelga and Cerezyme groups (if applicable). The implicit assumption of constant incidence rates over time will be evaluated.

Data will be analyzed as available, missing data will not be imputed. All summaries will be descriptive; no formal hypothesis testing will be performed.

As a part of exploratory analysis, specific analyses of the potential risks in the RMP and any new safety concern that could arise from the sub-registry will be conducted.

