## 7 RESEARCH QUESTION AND OBJECTIVES

### 7.1 PRIMARY OBJECTIVE

The primary objectives:

1. To evaluate the long-term safety of Cerdelga in real-world clinical practice.
2. To describe the utilization of Cerdelga.

The long-term safety of Cerdelga will be evaluated by the incidence rate of any AE during sub-registry participation, whether considered related or unrelated to Cerdelga by the treating HCP. The risk of an AE compared to Cerezyme will be evaluated in terms of the risk ratio (ratio of incidence rates).

Evaluation of utilization patterns of Cerdelga includes:

- To assess compliance/adherence of HCPs to the labelling with regard to CYP2D6 genotyping prior to initiation of Cerdelga
- To assess compliance/adherence of HCPs to the Cerdelga label with regard to patients' CYP2D6 predicted phenotype
- To assess compliance/adherence of HCPs to the Cerdelga label with regard to use in GD type 1.

In order to avoid the introduction of an element of positive or negative bias into the safety reporting from the ICGG Gaucher Registry physicians by providing a specific list of safety issues to be collected (and subsequently recorded in the CRFs) in protocol, there will be no suggested areas of safety data collection. Rather all safety data will be collected and subsequently assessed in relation to the important potential risks in the RMP. All AEs for Cerdelga and Cerezyme, regardless of their relation to treatment will be collected. However, when the safety analysis will be performed, specific exploratory analyses of the potential risks listed in RMP and any new safety concern that could arise from the sub-registry, will be included and reported in the PSUR in the EU regional annex.

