### **8.2.2 Eligibility criteria**

#### **8.2.2.1 Inclusion criteria**

Patients must meet the following criteria to be eligible to participate in the safety sub-registry:

- I 01. Male or female patient aged 18 years or older;
- I 02. The patient must be enrolled in the ICGG Gaucher Registry prior to safety sub-registry enrollment;
- I 03. The patient is willing and able to provide written informed consent for the safety sub-registry;
- I 04. The patient must have a confirmed diagnosis of GD, as defined in the protocol of the ICGG Gaucher Registry (documented acid  $\beta$ -glucosidase deficiency and/or mutations in the acid  $\beta$ -glucosidase gene);
- I 05. The patient must either initiate or continue treatment with Cerdelga or Cerezyme at the time of safety sub-registry enrollment.

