## **8.2.4 Modalities of recruitment**

### **8.2.4.1 Investigator selection**

The sub-registry study patients will be recruited from sites in countries where Cerdelga is already on the market or will become available on the market during the sub-registry enrollment period. Both ICGG Gaucher Registry sites and new sites, which could potentially become ICGG Gaucher

Registry sites, will be considered for the study. Health Care Providers at these sites who manage patients with GD1 will be invited to participate in the sub-registry.

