#### **8.8.1 Primary analysis**

- Incidence rate of any AE.
- Frequencies and percentages of timing of CYP2D6 genotyping (prior to or following) initiation of Cerdelga.
- Frequencies and percentages of CYP2D6 predicted phenotype among Cerdelga-treated patients.
- Frequencies and percentages of types of GD among Cerdelga-treated patients.

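### Among patients who started Cerdelga before enrollment, label adherence at initiation is measured only in those still treated, so it may be overstated; the utilization summaries need a defined denominator and a split by start date

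*Combined protocol and SAP*

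**What the plan says.** Section 7.1 makes utilization a primary objective and ties it to the decision to start. Its first part is "To assess compliance/adherence of HCPs to the labelling with regard to CYP2D6 genotyping prior to initiation of Cerdelga"; the other two concern predicted phenotype and use in type 1 disease. Section 6.2 says the results will help to judge whether the risk minimization measures work.

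The measures in Section 8.8.1 include "Frequencies and percentages of timing of CYP2D6 genotyping (prior to or following) initiation of Cerdelga" and "Frequencies and percentages of CYP2D6 predicted phenotype among Cerdelga-treated patients", with a matching summary for disease type. Sections 8.2.3 and 8.8 base analysis on the Safety Set: "all patients enrolled in the sub-registry who have received at least one dose of Cerdelga or Cerezyme following enrollment". Inclusion criterion I 05 reads: "The patient must either initiate or continue treatment with Cerdelga or Cerezyme at the time of safety sub-registry enrollment". Treatment status category (c) consists of "patients who were on treatment with the product of interest at entry into the sub-registry and then continue this therapy".

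Section 8.7.5 collects all past primary Gaucher treatments with dates, the start date of current treatment, the enrollment date and, if available, the genotype result and sampling date. Phenotype, disease history and treatment history carry a footnote: "Information collected as a part of ICGG Gaucher registry assessments". Section 8.10 does not mention selection by persistence on treatment.

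**The concern.** Adherence at initiation belongs to everyone who was started on the drug. For a patient started before enrollment, the plan observes that decision only if the patient was still on treatment when the sub-registry enrolled. A start in an ultra-rapid or indeterminate metabolizer, or in a patient without type 1 disease, that ended early is exactly the kind of failure risk minimization is meant to prevent. It is also the kind most easily lost from a group of continuing users.

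At stake is a primary result that goes to regulators as evidence on risk minimization. As planned, the tables would reveal neither the selection nor its direction.

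**Working it through.** **No adherence figure to reproduce.** The plan states no expected adherence, discontinuation rate or share of initiators. Its one probability statement (Section 8.6.1: more than 95% chance of at least one event in 100 patients at a 5% rate) is correct, since 1 − 0.95^100 = 0.994, but it plays no part here.

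**Where a label-discordant commercial start ends up:**

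| Patient's course | Reaches the adherence summaries? |
|---|---|
| Starts Cerdelga at enrollment | Yes |
| Enrolls on Cerezyme, switches to Cerdelga later | Can be; Section 8.8 evaluates data on each side of a switch |
| Started earlier, still on Cerdelga | Yes |
| Started earlier, now on Cerezyme | In the Safety Set with history collected, but no stated summary includes the start |
| Started earlier, now on neither product | Cannot enroll under I 05 |

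The gap is confined to the last two rows.

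**Do other provisions close it?** The Section 8.10 comparison is with registry patients who declined to join, where that information is obtainable; patients who had already stopped are not named. The tracking log in Section 8.7.4 is anonymous and holds only inclusion status and the reason for non-inclusion. The 3-month rule in Section 8.8 applies only when the patient's first Gaucher treatment was commercial Cerdelga or Cerezyme. A patient moved from another enzyme therapy to Cerdelga a few weeks before enrollment therefore appears to fall in category (c).

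**Size, on assumed inputs.** Let d be the true discordant share of starts, rd and rc the shares of discordant and concordant starters still on Cerdelga at enrollment, and f the share of the Cerdelga group initiating at enrollment.

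- Prevalent users show D = d·rd / [d·rd + (1 − d)·rc].
- The whole group shows f·d + (1 − f)·D.

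With d = 0.10:

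| rc | rd | D (f = 0) | f = 0.5 |
|---|---|---|---|
| 0.85 | 0.50 | 0.050/0.815 = 6.1% | 8.1% |
| 0.90 | 0.30 | 0.030/0.840 = 3.6% | 6.8% |
| 0.90 | 0.70 | 0.070/0.880 = 8.0% | 9.0% |
| 0.90 | 0.90 | 0.090/0.900 = 10.0% | 10.0% |
| 0.70 | 0.90 | 0.090/0.720 = 12.5% | 11.3% |

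At f = 1 every row returns 10%. With rc = 0.9 and rd = 0.5, adherence among prevalent users is overstated by 7.8, 4.2 and 2.2 percentage points when true adherence is 80%, 90% and 95%.

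**Effect of the undefined denominator.** Suppose 95 of 100 Cerdelga patients are adherent and 5 earlier starters are found in the Cerezyme group. Adding them gives 100/105 = 95.2% if none was discordant, 97.5/105 = 92.9% if half were, and 95/105 = 90.5% if all were.

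**The case against.** A reader might infer that adherence is judged only in patients persisting on Cerdelga, that stopped starts are never counted, and that adherence is therefore overstated. The documents do not support any of these in that strength.

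- I 05 admits patients who start at enrollment, and later switchers to Cerdelga can contribute. Neither group is selected by persistence.
- The Safety Set requires a dose of either product. A former Cerdelga patient now on Cerezyme can belong to it with treatment history recorded. Whether that patient counts as Cerdelga-treated is undefined, which is an ambiguity rather than an exclusion.
- Overstatement requires discordant starters to stop more often. That is plausible, since a late genotype result could end treatment, but the documents give no data on it.

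The three measures are also unequally exposed. A patient genotyped late and found within the labelled phenotypes has no stated reason to stop, and is then counted as genotyped after the start. Phenotype and disease type are more vulnerable.

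Site selection adds little. The text says "Health Care Providers at these sites who manage patients with GD1 will be invited to participate in the sub-registry", but the inclusion criteria require only confirmed Gaucher disease, with no restriction on type or phenotype.

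Finally, the parent registry's protocol and consent form are not available here, so its ability to supply the missing starts, and the sampling date in particular, cannot be confirmed.

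All of this stands and limits the point. What remains is the two unfilled rows in the table of patient courses and the silence of Section 8.10.

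**Conclusion.** The point holds for prevalent users. Their adherence at initiation is seen only if they were still treated at enrollment. Earlier discordant starts are excluded when the patient is on neither product, and are captured by no stated summary when the patient is on Cerezyme. Adherence in this group may be overstated.

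The size is illustrative only. At an assumed 10% true discordance and the three assumed patterns with more stopping among discordant starters, the reported share would be 3.6% to 8.0% if all patients were prevalent users, and about 6.8% to 9.0% if half were. Equal stopping removes the bias, the opposite pattern reverses it, and it shrinks as the share of initiators rises. The documents fix none of these inputs. The safety analyses are not affected by this point.

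**What to change.** In Sections 8.8.1 and 8.10:

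1. Report the three utilization summaries separately for patients who start Cerdelga at enrollment, after it, or within 3 months before it, whatever their prior Gaucher treatment, and for prevalent users. Treat the first group as the less selected estimate of adherence.
2. Define the adherence denominator as all commercial Cerdelga starts recorded in enrolled patients, including past starts in the Cerezyme group, using the treatment history already collected.
3. Where registry consent and data allow, add a separate column for ICGG Registry patients with a recorded commercial Cerdelga start who stopped before enrollment or did not join. Keep it apart from the main figures, because these records are not source-verified and the CYP2D6 sampling date may be missing.
4. State in Section 8.10 that starts stopped before enrollment are incompletely observed and that the direction of the resulting bias is unknown.

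Items 1, 2 and 4 need wording and a few extra descriptive tables from data already planned; the cost is smaller denominators per table. Item 3 depends on registry access that cannot be checked from these documents.

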#### **8.8.1 Primary analysis**

- Incidence rate of any AE.
- Frequencies and percentages of timing of CYP2D6 genotyping (prior to or following) initiation of Cerdelga.
- Frequencies and percentages of CYP2D6 predicted phenotype among Cerdelga-treated patients.
- Frequencies and percentages of types of GD among Cerdelga-treated patients.

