### **Study design**

This is a safety sub-registry of the ICGG Gaucher Registry (DIREGC07009).

This is a non-interventional, international, multicenter, prospective Post Authorization Safety Study (PASS) of Cerdelga, a treatment approved in many countries for adult patients with GD1 who have a CYP2D6 Poor Metabolizer (PM), Intermediate Metabolizer (IM), or Extensive Metabolizer (EM) phenotype. The study will enroll patients who will be receiving Cerdelga or Cerezyme for the first time or as part of ongoing treatment of their GD. At least 100 patients enrolled will be on Cerdelga. Patients will receive treatment as determined by the patient's HCP and guided by the provisions of the prevailing locally approved product labelling and educational materials, and the ICGG Gaucher Registry recommendations for patient monitoring.

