#### Important potential risks:

- Drug-drug interactions:
  - Use with CYP2D6 and/or CYP3A inhibitors
  - Use with strong CYP3A inducers
  - Use with P-gp or CYP2D6 substrates

- Use of Cerdelga in patients who are CYP2D6 indeterminate metabolizers or non-genotyped patients
- Cardiac conduction disorders and arrhythmias

Missing information:

- Use in patients with a history of or current cardiac ischemia or heart failure, clinically significant arrhythmias or conduction findings
- Use during pregnancy and lactation
- Safety in long-term treatment use
- Use in patients who are CYP2D6 URM

Available published and unpublished data related to gaps in knowledge reflect the current information presented above and in the EU RMP.

Additional pharmacovigilance activities beyond routine to gather long-term safety data are needed to explore and further characterize this missing information. As European Authorities have identified the limited number of exposed patients, particularly in real-world experience and in the long-term, as a major concerned area of research given that Cerdelga is intended to be a chronic treatment, long-term data will provide a better understanding of the potential risks that were identified in clinical studies and may clarify whether these risks are due to Cerdelga treatment, the underlying GD, or another cause.

Finally, the sub-registry will allow assessment of clinical practice and prescribing patterns, and the adherence of prescribing HCPs to Cerdelga key label (prescribing information) requirements, and will provide data to assess the effectiveness of risk minimization measures. Key prescribing information requirements include testing the genotype and predicting the phenotype of the key metabolic pathway, CYP2D6, in each patient before starting treatment to guide dosing; excluding CYP2D6 indeterminate and URM from treatment; and prescribing Cerdelga only to patients with type 1 GD.

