#### **8.4 STATISTICAL ANALYSIS**

Adverse events, SAEs, and events of interests will be summarized by treatment group, and by the three categories of treatment status and treatment group using percentage and frequency. For abnormal laboratory results assessed as AEs (clinically significant abnormal laboratory results), reported values of laboratory results in the course of AE follow-up will be summarized descriptively, including mean, standard deviation (SD), median, minimum and maximum. Categorical or qualitative variables will be summarized using percentages and frequency distributions. Timing of CYP2D6 genotyping and prevalence of CYP2D6 predicted phenotypes and GD subtype among Cerdelga-treated patients will be summarized using percentages and frequency.

In addition, the 95% confidence interval of incidence rates will be provided by treatment group. The risk of any AE in the Cerdelga group compared to Cerezyme will be evaluated in terms of the risk ratio with associated 95% confidence interval.

Data will be analyzed as available, missing data will not be imputed. For all AEs summary statistics, frequencies, cumulative incidence, and incidence rates per person-time will be calculated as appropriate. All summaries will be descriptive; no formal hypothesis testing will be performed.

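### The planned CYP2D6 phenotype table does not assess whether the recorded Cerdelga regimen in PM, IM and EM patients is consistent with the local label for their phenotype

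*Combined protocol and SAP*

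**What the plan says.** Section 7.1 makes the following part of the second primary objective: "To assess compliance/adherence of HCPs to the Cerdelga label with regard to patients' CYP2D6 predicted phenotype". Section 6.2 lists the key prescribing requirements. Genotype is tested and phenotype predicted for "CYP2D6, in each patient before starting treatment to guide dosing; excluding CYP2D6 indeterminate and URM from treatment", and use is confined to type 1 disease. The Study design paragraph of the Abstract gives the approved population as "adult patients with GD1 who have a CYP2D6 Poor Metabolizer (PM), Intermediate Metabolizer (IM), or Extensive Metabolizer (EM) phenotype".

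The analysis for this sub-objective is a single line in Section 8.8.1: "Frequencies and percentages of CYP2D6 predicted phenotype among Cerdelga-treated patients". Section 8.4 describes the same output: "Timing of CYP2D6 genotyping and prevalence of CYP2D6 predicted phenotypes and GD subtype among Cerdelga-treated patients will be summarized using percentages and frequency".

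The data on regimen are collected separately. Section 8.7.5 records at enrollment "Start date and dose of Cerdelga or Cerezyme treatment at sub-registry enrollment", and at each follow-up visit "Dosing information: including Cerdelga or Cerezyme regimen at the time of follow-up", together with longer interruptions, regimen changes and the reasons for them. No analysis section uses these items for the utilization objective.

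**The concern.** The objective concerns adherence, which compares what was prescribed with what the label asks for. The planned output describes the patients: how many treated patients fall in each phenotype. That is enough to judge whether Cerdelga was given to someone whose phenotype lies outside the approved population. It is not enough to judge whether a patient inside that population was put on a regimen consistent with the label for that phenotype.

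The second question is not remote from the protocol. Section 6.2 states that phenotype is predicted "in each patient before starting treatment to guide dosing", and gives assessing the effectiveness of risk-minimization measures as one use of the sub-registry. The final report could describe phenotype adherence from this table without having looked at the link between phenotype and regimen, although both variables are in the database.

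**Working it through.** **The plan's own figure.** The only design probability that can be recomputed is in Section 8.6.1: the chance of at least one patient with an event among 100 at a true cumulative rate of 5%. It is 1 − 0.95^100 = 0.994, which agrees with the stated value of more than 95%. It concerns adverse events and does not bear on this point.

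**Sections side by side.**

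| Label element (Section 6.2) | Planned output (Section 8.8.1) | Assessed? |
|---|---|---|
| Genotype tested before start | Timing of genotyping | Yes |
| Indeterminate and URM not treated | Phenotype counts in treated patients | Yes |
| Type 1 disease only | GD type counts in treated patients | Yes |
| Phenotype guides dosing | None | No |

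The timing table shows that a test preceded treatment, but not whether its result was reflected in the regimen.

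**Why the phenotype table cannot answer the last row.** Let n(p, r) be the number of Cerdelga patients with phenotype p on regimen r. The planned table reports only the row totals, n(p) = sum over r of n(p, r). Moving patients between regimens within a phenotype leaves every n(p) unchanged.

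As an illustration, assume that 96 of 100 Cerdelga patients are PM, IM or EM. The discordance rates are also assumptions, because the documents give none.

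| Assumed discordance | Discordant patients | Change in planned table |
|---|---|---|
| 0% | 0 | none |
| 5% | 96 × 0.05 = 4.8, about 5 | none |
| 10% | 96 × 0.10 = 9.6, about 10 | none |
| 20% | 96 × 0.20 = 19.2, about 19 | none |

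In all four cases the other 4 patients still appear in the table as URM or indeterminate.

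**Whether an added table would be informative.** These are exact (Clopper-Pearson) 95% intervals for a discordant proportion, assuming every patient can be classified. With 0 of n, the upper limit is 1 − 0.025^(1/n).

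- 0 of 100: 0 to 3.6%
- 5 of 100: 1.6% to 11.3%
- 10 of 100: 4.9% to 17.6%
- 20 of 100: 12.7% to 29.2%
- 0 of 80 (if only 80 can be classified): upper limit 4.5%

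At the planned size, the result would separate rare discordance from common discordance.

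**Whether the data exist.** Section 8.7.5 collects the genotype result (if available), dose at enrollment, doses of past primary GD treatments, and regimen and its changes at follow-up. Concomitant medication is collected only in particular cases (table footnote d of Section 8.7.5).

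**The case against.** The strongest defense is that the plan is internally matched. Section 6.2 lists three requirements, Section 7.1 lists three adherence sub-objectives, and Section 8.8.1 has three utilization tables, one for each. On this reading the phenotype sub-objective means the exclusion rule, which the planned table checks directly, and the reference to dosing only explains why testing comes first. No objective names dose adherence. The documents also reproduce no label, so how far regimens could depart from it cannot be checked here.

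Much of this stands. The mapping is real, and the exclusion rule is covered. But Section 7.1 does not limit the phenotype sub-objective to exclusion, and guiding dosing is the use of phenotype that Section 6.2 itself states. The absence of label text limits what can be said about size. It does not change the fact that the planned table is insensitive to regimen.

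Three stronger readings are tempting, and the documents do not support them.

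- A reader might infer that prescribing against phenotype goes undetected altogether. It does not: the table's denominator is treated patients, so treated URM and indeterminate patients are counted. Doses above the authorized maximum are also reportable as overdoses even without an adverse event (Section 10.1.2), although as individual cases and not as an adherence measure.
- A reader might infer that a fixed share of the phenotype requirement is unmeasured. The text does not divide the requirement into measured portions.
- A reader might infer that the plan would report an inflated adherence percentage. It defines no adherence percentage, and the documents hold no figures from which an inflation could be computed.

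**Conclusion.** The point holds in a limited form. For PM, IM and EM patients, consistency of the recorded regimen with the local label for their phenotype is not assessed, although the protocol ties phenotype to dosing and collects the regimen. The planned table does cover use outside the approved phenotypes, and patients of unknown phenotype if missing values are shown as a row.

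The size is unknown. The discordance rates and the 96-patient split above are illustrations only. The consequence is an incomplete answer to one part of the second primary objective. It does not affect the sample size, the adverse event rates or the comparison with Cerezyme. This is an inexpensive improvement to a descriptive plan, not a flaw that undermines the study. No view is taken on which regimen is right for any phenotype.

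**What to change.** Add to Section 8.8.1 a descriptive cross-tabulation of predicted phenotype by recorded Cerdelga regimen. Produce it at sub-registry enrollment (at initiation where that dose is available) and at each recorded regimen change. For each, give the number and percentage of patients who are concordant, not concordant or not classifiable against the locally approved label in force on that date. Show missing phenotype as its own category. State the classification rule and the label versions used before the final analysis. A confidence interval is optional, because Section 8.4 plans intervals only for incidence rates and the risk ratio.

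The costs are one derived variable, one table and a label lookup by country and date. No new data collection is required, but there are two limits. Dose at initiation may be missing for patients already on treatment at entry. Where the label makes the regimen depend on interacting medicines, the partial collection of concomitant medication means that concordance cannot be fully classified. A footnote to the table should say so.
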